4.2.2.6 Treatment interruptions, duration (days) of interruptions, and the reason for interruptions

Definition of treatment interruption:

- Short interruptions (defined as the durvalumab infusion interruption during the administration recorded in CRF in a single visit) are excluded from this analysis.
- Treatment withheld is defined as temporarily withheld of durvalumab recorded in CRF. It is possible that patients have durvalumab withheld in one visit and resumed in later visit and have multiple treatment withholds.

The duration of interruption will only include treatment withheld. Short interruption which resumed during the same visit will not be included in the calculation for duration of interruption. Start and end date of duration of interruption are defined as follows:

- Start date will be defined as the date of durvalumab withheld recorded in the CRF.
- End date will be defined as the earliest of:
 - Subsequent date of non-zero dose administration of durvalumab
 - Permanent discontinuation
 - Date of study exit
 - Death date

Since it is possible for patients to experience multiple treatment withholds/resumptions, the duration of interruption will be sum of the duration of each withheld/resumption.

The duration is calculated as:

Duration (days) of interruption = \sum (End date as described above – Start date of treatment withheld + 1)

Where there are only limited number of treatment interruptions, listing will be provided as stated in section 4.2.4.6.

Where there are sufficient number of treatment interruptions, frequency and percentage of patients with treatment withheld, reason of treatment withheld, and duration of interruption will be summarized.

4.2.2.7 Time (days) to development of Grade 3 to 5 AEs, including pneumonitis

Time (days) to development of Grade 3 to 5 pneumonitis AEs is defined as the period from Day 1 to earliest of each grade of pneumonitis AE (grade 3, grade 4, and grade 5) or censoring date using the following rules:

- Date of study exit for patient who did not experience the event and left the study during the period of follow-up.
- End of the period of follow-up for patient who did not experience the event and remained in the study after the period of follow-up.

Where there are only limited number of pneumonitis AEs, listing will be provided as stated in section 4.2.1.

Where there are sufficient number of pneumonitis AEs, time to development of Grade 3 to 5 pneumonitis AEs will be summarized using Kaplan-Meier summary statistics including 1st quartile and 3rd quartile time to event, median time to events with 95% CIs, the number of events, the number of censored.

This analysis will be repeated for pulmonary AEs (section 4.2.2.1).

4.2.2.8 Prescription of medication used to manage pulmonary AEs and duration (days) of treatment

This endpoint is fulfilled by section 4.2.4.5.

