3.2 Study Endpoints

The endpoint used to address the primary objective is:

- Occurrence of pneumonitis (either radiation or immune-mediated, by grade).
 - Grade of pneumonitis at diagnosis and highest grade of pneumonitis

The endpoints used to address the secondary objectives are:

- Occurrence of pulmonary AEs, including diagnoses of events, by grade
- Duration (days) of pulmonary AEs by type and grade
- Permanent discontinuation of durvalumab due to pulmonary AEs, including pneumonitis
- Early discontinuation of durvalumab treatment for any reason
- Duration (days) of durvalumab treatment
- Treatment interruptions, duration (days) of interruptions, and the reason for interruptions that will be captured in a standard data management form with the site physician documenting reasons in patient charts
- Time (days) to development of Grade 3 to 5 AEs, including pneumonitis

- Prescription of medication used to manage pulmonary AEs and duration (days) of treatment
- Change in QoL scores from baseline

The endpoints used to address the exploratory objectives are:

CCI

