6 VARIABLES AND EPIDEMIOLOGICAL MEASUREMENTS

6.1 Patient Characteristics

The following information will be obtained at Baseline:

- Demographic variables (as allowed by local regulations):
 - Age
 - Date of data collection
 - Sex
- Current physiological variables:
 - Height (inches)
 - Weight (pounds)
 - Temperature
 - Blood pressure
 - Heart rate (beats per minute)

- Respiratory rate
- Oxygen saturation (pulse oximetry)
- Pulmonary function tests including: FEV₁, FVC, FEV₁/FVC ratio: obstructive versus restrictive, and peak expiratory flow (PEF)
- Comfort and familiarity with technology, including, but not limited to, internet use, ownership of smartphones, email use, etc.
- Relevant concomitant medications including, but not limited to, respiratory medications
- Abbreviated medical history (from birth to Baseline visit)
- Relevant previous respiratory medical history or procedures including, but not limited to, thoracentesis, subsequent radiation, etc.
- Disease characteristics, such as date of diagnosis, stage at diagnosis, current stage, etc.
- Previous treatments for NSCLC, including sequential CRT, cCRT regimen for unresectable Stage III NSCLC
- Time since most recent radiation

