7.4.6 Durvalumab Treatment

Throughout the study, updated information on the patients' durvalumab treatment will be collected, including durvalumab start and stop date, treatment holds, interruptions, and permanent discontinuations (including reasons for each), as well as details regarding other treatments such as chemotherapy and radiation therapy (including doses and number of cycles).

Concomitant medication (including over-the-counter medication) details will also be collected. The indication for treatment must be recorded, including drug name, route, and duration of drug administration.

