3.2 Missing Data

For AEs and concomitant medications with missing start and/or end dates, the following rules will be applied:

For medication and AE, imputation of end date is not necessary if it is ongoing. If the ongoing flag is missing, then assume that AE is still present/medication is still being administered (i.e., do not impute a date).

Check the data captured in the following fields in the CRF:

- “Was this medication taken as a result of an adverse event”
If the response is “yes”, concomitant medication partial/missing start/end dates can be imputed by referring to related AE number, and vice versa.
- “Was this taken for a condition reported as medical history”
If the response is “yes”, concomitant medication partial/missing start/end dates can be imputed by referring to related medical history number.

If the responses to the above questions are “no” or do not allow imputed values, the following rules will be applied:

Partial/missing start date:

- Missing day - impute the first day of the month unless month is same as month of Day 1 then impute date of Day 1.
- Missing day and month – impute 1st January unless year is the same as Day 1 then impute date of Day 1.
- Completely missing – impute date of Day 1 unless the end date suggests it could have started prior to Day 1 in which case impute the 1st of January of the same year as the end date.
- When imputing a start date ensure that the new imputed date is sensible i.e., it is prior to the corresponding end date if known.

Partial/missing end date:

- Missing day - impute the last day of the month unless month is same as month of study exit then impute date of study exit.
- Missing day and month – impute 31st December unless year is the same as date of study exit then impute date of study exit.
- Completely Missing – For the concomitant medication, if start date is prior to Day 1 then impute date of Day 1, if it started on or after Day 1 then follow the above rule for missing day and month. For the adverse event, the end date will not be imputed.
- Note - for AE, duration would not be calculated.

These imputed dates will be used to determine whether the AEs are treatment emergent or if medications are concomitant. Missing safety data will be treated as missing. However, safety assessment values of the form of “< x” (i.e., below the lower limit of quantification) or > x

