3.3 Study Endpoints

The definition and analysis of endpoints listed below are described in detail in section 4.2.

The endpoint used to address the primary objective is:

[figure not shown]
- Occurrence of pneumonitis (either radiation or immune-mediated, by grade).
 - Grade of pneumonitis at diagnosis and highest grade of pneumonitis

The endpoints used to address the secondary objectives are:

- Occurrence of pulmonary AEs, including diagnoses of events, by grade
- Duration (days) of pulmonary AEs by type and grade
- Permanent discontinuation of durvalumab due to pulmonary AEs, including pneumonitis
- Early discontinuation of durvalumab treatment for any reason
- Duration (days) of durvalumab treatment
- Treatment interruptions, duration (days) of interruptions, and the reason for interruptions that will be captured in a standard data management form with the site physician documenting reasons in patient charts
- Time (days) to development of Grade 3 to 5 AEs, including pneumonitis
- Prescription of medication used to manage pulmonary AEs and duration (days) of treatment
- Change in QoL scores from baseline

The endpoints used to address the exploratory objectives are:

CCI

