4.2.4.5 Prior and Concomitant Medications

Prior medications are medications taken before baseline and include medications ongoing at the start of durvalumab. Concomitant medications are medications taken on or after baseline. For medications with incomplete end dates, the imputed dates will be used to determine if the medications are concomitant. If a patient has taken a medication more than once, the patient will be counted only once in the total.

The summary of medications taken during the course of the study will be presented in tabular form using Anatomical Therapeutic Chemical (ATC) classification level 2 and generic drug name via the WHO Drug Global B3 Sep 2019 or later. All medications will be sorted alphabetically by ATC level 2 class and generic drug name. A listing of concomitant medications will be presented.

Concomitant procedures collected in CRF will be also presented in the listing.

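### The SAP specifies no summary of medication used for pulmonary AEs or of its duration, and contradicts itself on the scope of time to Grade 3 to 5 AEs

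*SAP*

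**What the plan says.** **Medication endpoint.** SAP 3.3 lists "Prescription of medication used to manage pulmonary AEs and duration (days) of treatment" among the secondary endpoints and states that section 4.2 holds the definitions and analyses. The whole of SAP 4.2.2.8 is the sentence "This endpoint is fulfilled by section 4.2.4.5". Section 4.2.4.5 defines prior and concomitant medication, counts a patient once per medication, and then says: "The summary of medications taken during the course of the study will be presented in tabular form using Anatomical Therapeutic Chemical (ATC) classification level 2", together with generic drug name. It adds listings of concomitant medications and procedures, without naming their columns.

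The raw material exists. Protocol 7.4.6 says "The indication for treatment must be recorded, including drug name, route, and duration of drug administration". The CRF, as described in SAP 3.2, asks whether a medication was taken because of an AE and links it to an AE number.

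**Time to Grade 3 to 5 AEs.** Protocol 3.2 gives the endpoint as "Time (days) to development of Grade 3 to 5 AEs, including pneumonitis". SAP 3.3 repeats it, and SAP Table 1 assigns Kaplan-Meier to it; neither restricts the type of AE. SAP 4.2.2.7 defines the time variable for pneumonitis and repeats it for pulmonary AEs, which section 4.2.2.1 ties to the term list in section 8.3.

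**The concern.** In a single-arm pilot with no formal testing, the specified tables and listings are the result. Protocol 4.2 also counts positive findings on the secondary endpoints among the factors for moving to a larger trial. An endpoint whose analysis is only a pointer to a general table leaves the selection of drugs and the counting of days to whoever programs or reads the output, after the data have been seen. An endpoint with one scope in the endpoint list and Table 1 and a narrower one in its own section can be reported either way.

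**Working it through.** No figure in the plan bears on this point, so the check sets each endpoint beside the text meant to deliver it.

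**1. Medication endpoint**

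| Component | What SAP 4.2.4.5 specifies |
|---|---|
| Medication used for pulmonary AEs | A table by ATC level 2 and generic name; no selection by AE or indication |
| Days of treatment | Nothing: no start and end rule, no formula, no summary statistic |
| Listing | Concomitant medications; columns not stated |

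- *The AE link is not used for this purpose.* SAP 3.2 says "concomitant medication partial/missing start/end dates can be imputed by referring to related AE number", and then "These imputed dates will be used to determine whether the AEs are treatment emergent or if medications are concomitant". The link serves date imputation, and the stated use of the imputed dates is classification.
- *Ongoing treatment has no end.* SAP 3.2 imputes no end date for an ongoing medication, and no censoring rule is given. Days of treatment are therefore undefined for a drug still being taken at study exit.
- *The other durations are defined.* AE duration (4.2.2.2), durvalumab treatment (4.2.2.5) and interruptions (4.2.2.6) each have a start, an end and a formula. Medication has none, and the endpoint has no row in SAP Table 1.
- *Baseline drugs mix in.* Protocol 6.1 collects "Relevant concomitant medications including, but not limited to, respiratory medications" at Baseline. A respiratory drug already in use and continued would enter the same table as one started for a pulmonary AE.

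**2. Time to Grade 3 to 5 AEs**

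| Place | Scope |
|---|---|
| Protocol 3.1 and 3.2; SAP 1.1.2 and 3.3 | Grade 3 to 5 AEs, pneumonitis included; no pulmonary qualifier |
| SAP Table 1 | Grade 3 to 5 AEs, Kaplan-Meier, no restriction |
| SAP 4.2.2.7 | Pneumonitis (six terms, section 8.2), then pulmonary AEs (37 terms, section 8.3) |
| SAP 4.2.4.8 | All AEs: frequencies by CTCAE grade and listings; no time to onset |
| SAP 6, visible text | Changes to logistic regression, full analysis set and QoL; nothing on this endpoint |

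Neighbouring secondary endpoints carry the word pulmonary and this one does not. Table 1 names a method for the unrestricted endpoint, but section 4.2 holds no matching event definition or censoring rule. An AE term in neither list, such as plain pneumonia, has no defined time to onset.

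**3. Size**

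The documents give no rate of medication use for pulmonary AEs and no overall Grade 3 to 5 AE rate, so neither gap can be counted in patients. One figure gives context only. If the Grade 3 or 4 pneumonitis rate of 3.4% quoted in Protocol 2.2 applied, 75 × 0.034 = 2.55 patients would be expected. The pneumonitis part of 4.2.2.7 would then probably appear as a listing. That figure does not measure what is missing.

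**The case against.** **Listings exist.** A reader might infer that the SAP yields nothing at all on medication for pulmonary AEs. The documents do not support that. Section 4.2.4.5 promises a listing, the dates and the AE link are collected, and listings are this SAP's planned output elsewhere when events are few. What stands is narrower: no summary is specified, the listing's columns are not stated, and a hand count is not a pre-specified analysis.

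**The data may already be pulmonary-related.** The row in Protocol Table 1 and the End-of-Study text in Protocol 7.1.2 speak of pulmonary-related concomitant medication, so the 4.2.4.5 table may not pool every drug. Protocol 7.4.6 and the footnote to that row read more broadly, so the scope is unclear. Even a collection limited to pulmonary-related drugs would not separate drugs given for an AE from those in use at Baseline, and would give no duration.

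**A pulmonary scope may have been meant.** The version history for Amendment 2 says the secondary objectives were revised to focus on pulmonary AEs. That makes a pulmonary-only reading of the Grade 3 to 5 endpoint plausible. With the unrestricted row in SAP Table 1, it means the second part is an internal inconsistency and not a clean omission. Part of SAP section 6 is also redacted, so a declared change there cannot be excluded. The mismatch between 3.3, Table 1 and 4.2.2.7 remains on either reading.

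**Pneumonia.** A reader might infer that the protocol collects details of pneumonia itself. The row in Protocol Table 1 uses a diagnosis of pneumonia or pneumonitis as the trigger for collecting details of pneumonitis. Pneumonia therefore serves here only as an example of a term in neither list.

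**Other endpoints.** It is tempting to extend the point to discontinuation due to pulmonary AEs and to QoL change. Reasons for stopping treatment are tabulated under 4.2.4.1 and AEs leading to discontinuation are listed under 4.2.4.8. The QoL restriction is disclosed in section 6. Neither is part of this finding.

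**Conclusion.** The point holds in two parts of unequal strength.

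1. *Medication endpoint: firm.* Section 4.2.2.8 relies on a section that specifies neither component of the endpoint. Followed as written, the SAP gives no summary of which drugs were used for pulmonary AEs or for how long. Sections 4.2.2.8 and 4.2.4.5 show no redaction.
2. *Time to Grade 3 to 5 AEs: an inconsistency to resolve.* The endpoint list and Table 1 are unrestricted and the defining section is not. This rests on the visible text of section 6 and leaves open which scope was intended.

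A reader might try to size the problem with the 33.9% any-grade pneumonitis rate in Protocol 2.2. That rate counts pneumonitis, not patients medicated for a pulmonary AE, so it does not measure the gap. The change is worth making because it is cheap and concerns stated secondary endpoints. It does not affect the primary endpoint or the sample size.

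**What to change.** **SAP 4.2.2.8.** Replace the cross-reference with an analysis:

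- select medications linked by CRF AE number to a pneumonitis AE and, separately, to another pulmonary AE;
- report n and % of patients by drug;
- define duration = end date (or date of study exit or death, if ongoing) − start date + 1, and say whether imputed dates are used;
- summarise duration and state how many treatments were ongoing, or list it with the linked AE if events are few.

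Add the matching row to SAP Table 1.

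**SAP 4.2.2.7.** Choose one:

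- add time from Day 1 to the first Grade 3 to 5 treatment-emergent AE of any type, with its censoring rule, and keep the pneumonitis and pulmonary versions; or
- if a pulmonary scope was intended, declare it in section 6 and align SAP 3.3 and Table 1 with 4.2.2.7.

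**Cost.** SAP text and one or two tables from data already collected (AE link, medication dates, AE grade and onset date). No new data and no extra patients.

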4.2.2.9 Change in QoL assessment scores from baseline

Quality of life assessment questionnaires will be conducted at Baseline visit, every 2 weeks for the first 3 months and once monthly thereafter, and at End-of-Study visit. The questionnaires will include European Organization for Research and Treatment of Cancer Quality of Life Core Questionnaire (EORTC QLQ C30) and Lung Cancer Module (EORTC QLQ LC13). EORTC QLQ C30 will be separated into 3 parts, function scales, symptoms scales and global health status (GHS) [1]. EORTC QLQ LC13 will be measured by 3 parts including lung cancer associated symptoms (cough, haemoptysis, dyspnea, and site-specific pain), treatment-related side effects (sore mouth, dysphagia, peripheral neuropathy and alopecia) and pain medication [2].

Therefore, the assessment scores by these two QoL questionnaires will be summarized by 6 parts as following:

- Part 1: Function scales from EORTC QLQ C30; Higher score signifies higher functional ability (i.e. better quality of life); Item 1-7 and Item 20-27
- Part 2: Symptom scales from EORTC QLQ C30; Higher score signifies stronger symptoms (i.e. worse quality of life); Item 8-19 and Item 28
- Part 3: GHS from EORTC QLQ C30; Higher score signifies higher GHS (i.e. better quality of life); Item 29-30
- Part 4: Lung cancer associated symptoms from EORTC QLQ LC13; Higher score signifies stronger symptoms (i.e. worse quality of life); Item 31-35 and Item 40-42
- Part 5: treatment-related side effects from EORTC QLQ LC13; Higher score signifies stronger side effects (i.e. worse quality of life); Item 36-39
- Part 6: Pain medication from EORTC QLQ LC13; Higher score signifies better pain relief from medication; Item 43

Time windows below will be used to summarize scores by planned data collection time points:

Week	Day	Statistical Analysis Window
Baseline	Day 0	Low – <1
Week 2	Day 11	1 - 21

Week 4	Day 28	22 - 35
Week 6	Day 42	36 - 49
Week 8	Day 56	50 - 63
Week 10	Day 70	64 - 77
Week 12	Day 91	78 - 105
Month 4	Day 120	106 - 135
Month 5	Day 150	136 - 165
Month 6	Day 180	166 - 195
Month 7	Day 210	196 - 225
Month 8	Day 240	226 - 255
Month 9	Day 270	256 - 285
Month 10	Day 300	286 - 315
Month 11	Day 330	316 - 345
Month 12	Day 360	346 - 375

- Inclusion within the time window will be based on the actual date and not the intended data collection time point.
- If there are two scores recorded on the same day, the average of the two records will be used.

If there are limited number of patients with AE events, figure will be produced to show the score change through all time windows with 1 line per patient along with the following labels for AE groups: pneumonitis AEs, other pulmonary AEs.

[figure not shown]
Where there are sufficient number of patients with AE events, the score change from baseline for the scores within time windows at specified time points will be summarized by part and by CTCAE grade (only AEs which has causal relation with durvalumab), mean score change, standard deviation, median, minimum, maximum, and along with the number of patients. The time points are:

- Time Point 1: Prior to the time window which initial pulmonary AE occurred.
- Time Point 2: At the same time window which initial pulmonary AE occurred.
- Or other time point(s) if necessary.

[figure not shown]
The 95% CI of mean score change will be calculated by one-sample t distribution / z distribution depending on sample size. This analysis will be repeated for pneumonitis AEs

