7.4.2 Symptom Assessments

Pulmonary function data collected via mobile applications and devices are described in Table 3.

Table 3 Data Collected via the Current Wearable Health Monitoring System

Pulmonary Function Parameters	Lowest Acceptable Value*
FEV ₁	LLN
FVC	LLN
FEV ₁ /FVC ratio	LLN
Oxygen saturation	90%
PEF	LLN

FEV₁ = forced expiratory volume; FVC = forced vital capacity; LLN = lower limit of normal; PEF = peak expiratory flow

* Measurements less than the LLN indicate the presence of an abnormality

Study physicians should review values lower than normal on a daily basis in alignment with regular business hours (as noted above) and patients will be contacted if clinical intervention is necessary.

Patients will be advised to contact their treating physicians if they develop any of the following symptoms from either a change of baseline or a new worsening symptom that needs to be reported as a potential AE/serious adverse event (SAE): trouble breathing, chest pain, new or worsening cough, productive cough with purulent secretions, shortness of breath, fever, or tachycardia.

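### The secondary QoL analysis reports change only by six questionnaire parts, with no part-scoring rule and no separate dyspnoea or cough change score, so a respiratory change around a pulmonary AE may be diluted.

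*SAP*

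**What the plan says.** SAP 4.2.2.9 covers the secondary endpoint of QoL change from baseline, measured with the EORTC QLQ-C30 and QLQ-LC13. It states that "the assessment scores by these two QoL questionnaires will be summarized by 6 parts as following". The two symptom parts that matter here are:

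- Part 2: "Symptom scales from EORTC QLQ C30; Higher score signifies stronger symptoms (i.e. worse quality of life); Item 8-19 and Item 28".
- Part 4: "Lung cancer associated symptoms from EORTC QLQ LC13; Higher score signifies stronger symptoms (i.e. worse quality of life); Item 31-35 and Item 40-42". The same section describes its content as "lung cancer associated symptoms (cough, haemoptysis, dyspnea, and site-specific pain".

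With enough AEs, change from baseline around the event is "summarized by part and by CTCAE grade (only AEs which has causal relation with durvalumab"; the analysis is set out for pulmonary AEs and repeated for pneumonitis. With few AEs, a "figure will be produced to show the score change through all time windows with 1 line per patient", without saying which score is drawn.

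The objective served (Protocol 3.1, SAP 1.1.2) is to describe QoL and how it relates to AEs. Protocol 7.4.2 lists the symptoms that should prompt a patient to contact the treating physician: "trouble breathing, chest pain, new or worsening cough, productive cough with purulent secretions, shortness of breath, fever, or tachycardia".

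**The concern.** Trouble breathing, shortness of breath and cough are on the protocol's own list of symptoms to report. The SAP names dyspnoea and cough as distinct content of the LC13, yet its reporting unit is the part. On the most natural reading, a table of Part 4 change around a pneumonitis event cannot show whether breathing or cough moved, or whether a small net change hides worse breathing with less pain.

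What is at stake is the secondary objective. Protocol 4.2 says that secondary findings feed the decision on a larger trial, so a muted QoL signal in this pilot could be misread. The primary endpoint, occurrence of pneumonitis by grade, is not affected.

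**Working it through.** **1. The plan's own figure.** Counting the item ranges in SAP 4.2.2.9:

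- QLQ-C30: Part 1 (items 1-7, 20-27) = 7 + 8 = 15; Part 2 (8-19, 28) = 12 + 1 = 13; Part 3 (29-30) = 2. Sum 30.
- QLQ-LC13: Part 4 (31-35, 40-42) = 5 + 3 = 8; Part 5 (36-39) = 4; Part 6 (43) = 1. Sum 13.

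The parts cover items 1 to 43 once each, with no gap or overlap. The split is internally consistent.

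**2. Is each part one score?** No formula is given. The only averaging mentioned in the section concerns two scores recorded on the same day. For one score per part: one item list, one direction, and tables by part. Against it: Parts 1 and 2 use the plural word scales, so the parts could be headings over several scales. Under that second reading the SAP does not say which scales are reported. Both readings need the same clarification.

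**3. Dilution if a part is one equally weighted score.** Assumptions: equal item weights; cough plus dyspnoea on k of the m = 8 items in Part 4, with k from 2 to 6, because the documents do not give items per symptom; other items unchanged. The 20-point change is illustrative.

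Part change = 20 × k/m. The standardised effect, relative to a separate cough-plus-dyspnoea score, is (k/m) × √{[(1+(k−1)r)/k] / [(1+(m−1)r)/m]}, assuming equal item SDs and common correlation r.

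| k of 8 | Change seen in Part 4 | Relative standardised effect, r = 0.3 |
|---|---|---|
| 2 | 20 × 2/8 = 5.0 | 0.32 |
| 4 | 20 × 4/8 = 10.0 | 0.55 |
| 6 | 20 × 6/8 = 15.0 | 0.78 |

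Over r = 0 to 0.7 and k = 2 to 6 the relative effect runs from 0.27 to 0.87. If the four named symptoms are weighted equally instead, the change is 20 × 2/4 = 10 points.

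For Part 2 (m = 13), a 20-point change on a single item would show as 20/13 = 1.5 points. How many Part 2 items are respiratory is not stated.

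**4. Offset by pain.** Assume also that haemoptysis takes one item and does not move, which leaves 7 − k items for pain. Part 4 shows no change if pain improves by 20k/(7 − k): 40/5 = 8 points at k = 2, and 80/3 = 26.7 points at k = 4. At k = 6 it would need 120/1 = 120 points, more than a 0-100 scale (assumption) allows. Full cancellation is therefore possible for some item splits only. Partial offset is possible for all of them.

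**The case against.** **No scoring rule is stated, so pooling is an inference.** A reader might take it as fact that items are averaged within parts. The documents do not say so. This stands, and the sizes above are therefore conditional. The missing rule is itself part of the point.

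**Other text may report these scores.** A reader might conclude that dyspnoea and cough are never reported. That cannot be shown. SAP 4.2.3 is redacted, the Data Analysis Plan cited in SAP 1.1.3 is not visible, and Protocol 9.3.1 allows lagged PRO values as model covariates. However, none of the four exploratory headings in the SAP contents is titled as a QoL summary, and the secondary endpoint is defined in 4.2.2.9. Use of PROs in an exploratory model would not fill the gap there.

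**Pain may be relevant.** A reader might call the pooled items unrelated to pneumonitis. The Part 2 items are not named in the documents, and chest pain is on the list in Protocol 7.4.2. This stands, but it favours separate scores, which would show which symptom moved.

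**Detection is a different analysis.** A reader might infer that the six parts would make PROs look useless as pneumonitis predictors. SAP section 6 places those models under exploratory endpoints outside the SAP's coverage, and nothing visible says that they use the six parts. The point is confined to the secondary description.

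**Scale of the study.** This is a 75-patient pilot without a power basis (SAP 1.3) and with descriptive analyses only (SAP 4.1). Respiratory function is also measured daily by the devices. This limits the seriousness of the point, but the QoL objective still needs an analysis that can describe it.

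**Conclusion.** The point holds as a cheap improvement to a secondary descriptive analysis. The documents establish the six-part reporting unit, the grouping of cough and dyspnoea with haemoptysis and pain in Part 4, the absence of a part-scoring rule, and the absence of a separate dyspnoea or cough change score in the visible secondary analysis.

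The size is illustrative. Under one equally weighted score per part, 25% to 75% of a change confined to cough and dyspnoea survives in Part 4 (2/8 to 6/8), or half under equal symptom weights. A reader might be tempted by a steeper figure that counts dyspnoea alone on 1 to 3 of 8 items (13% to 38%). That leaves out cough, and the item counts are not in the documents. The signal would be diluted and open to offset, but not necessarily lost.

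**What to change.** In SAP 4.2.2.9:

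1. State how each of the six parts is scored: which items or scales enter, with what weights, and whether a part yields one score or several.
2. Add change from baseline in the LC13 dyspnoea and LC13 cough scores, and in any separate dyspnoea score within the C30 symptom scales, to the pulmonary-AE and pneumonitis summaries. Keep the six parts alongside.
3. For the few-events case, say which scores the patient-line figure shows, and include dyspnoea and cough panels.
4. If the Data Analysis Plan already reports these scores, cross-reference it in place of steps 2 and 3.

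The cost is SAP wording and a few more descriptive rows and panels from questionnaires already collected. No formal testing is planned, so there is no multiplicity cost.
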